**Family 1: Non-inferiority of rMenB+OMV NZ + PCV13 to PCV13 with respect to GMCs at one month post 3rd vaccination**

Non-inferiority will be claimed if the following null hypothesis will be rejected for the 13 PCV13 antigens:

$$H_{01j}: \mu_{Aj} - \mu_{Bj} \leq \delta \text{ vs. } H_{11j}: \mu_{Aj} - \mu_{Bj} > \delta, j=1,..13,$$

where  $\delta$  denotes the non-inferiority margin ( $\log_{10}(0.5)$ ),  $\mu_A$ , and  $\mu_B$  denote the means of log 10-transformed concentrations at one month after the 3rd vaccination from Group MenB+PCV and Group Placebo+PCV, respectively, and  $j$  refers to the 13 antigens.

**Family 2: Percentage of subjects with hSBA titers  $\geq 8$  (for strains M14459, NZ98/254, M13520) and  $\geq 16$  (for strain 96217) and the composite endpoint, at one month post-4th vaccination**

Sufficiency will be claimed for each of the 4 test strains and the composite endpoint, separately, if the following null hypothesis will be rejected:

$$H_{02j}: P_{Aj} < A_j \text{ vs. } H_{12j}: P_{Aj} \geq A_j,$$

where  $P_{Aj}$  denotes the percentage of subjects with hSBA titers  $\geq 8$  (for strains M14459, NZ98/254, M13520) and  $\geq 16$  (for strain 96217) at one month after the 4th vaccination for strain  $j$ , ( $j=1, 2, 3, 4$ , and composite).  $A_j$  represents the level of sufficient immune response for each of the four strains and composite endpoint. The immune response at one month following the 4th vaccination, will be sufficient for rMenB+OMV against each individual strain if the lower limit of the alpha-adjusted CI for the percentage of subjects with hSBA titers  $\geq 8$  (for strains M14459, NZ98/254, M13520) and  $\geq 16$  (for strain 96217) is  $\geq 75\%$  for the individual *N. meningitidis* serogroup B test strains, and is  $\geq 65\%$  for the composite endpoint.

**Family 3: Percentage of subjects with hSBA $\geq$ LLOQ for each of the four strains (M14459, 96217, NZ98/254, M13520) and the composite endpoint, post-3rd, one month post post-3rd. vaccination**

Sufficiency will be claimed for each of the 4 strains and the composite endpoint, separately, if the following null hypothesis will be rejected:

$$H_{03j} : P_{Aj} < A_j \text{ vs. } H_{13j} : P_{Aj} \geq A_j,$$

[figure not shown]
where  $P_{Aj}$  denotes the percentage of subjects  $hSBA \geq LLOQ$  at one month after the 3rd vaccination for strain  $j$ ,  $j=1, 2, 3, 4$ , and composite.  $A_j$  represents the level of sufficient immune response for each of the four strains and composite endpoint. The immune response at one month following the 3rd vaccination, will be sufficient for rMenB+OMV NZ against each individual strain if the lower limit of the alpha-adjusted CI for the percentage of subjects with  $hSBA$  titer  $\geq LLOQ$  is  $\geq 60\%$  for the *N. meningitidis* serogroup B test strains, and  $\geq 50\%$  for the composite endpoint.

#### Statistical Methods

For statistical analyses of the concentration/titer data, the concentrations/titers will be logarithmically transformed (base10), to fulfil Gaussian distribution assumption.

The Global Type I error rate will be controlled globally at a 5%/2.5% level (2-/1-sided, respectively). If applicable, the  $\alpha$ -level will be propagated as described below [Bretz et al., 2009]. The sequence of testing the different families is presented in [Figure 2](#) and described in more detail thereafter.

**Figure 2 Testing Strategy for Three Families with Corresponding  $\alpha$  Propagation**

The initial  $\alpha$  is 0.0167 (2-sided) for Family 1 and 0.0333 (2-sided) for Family 2, while it is zero for family 3.

**Step 1: Family 1 and Family 2**

- i. Start test Family 1 and Family 2 as the first step.
  - For testing Family 1 the hypotheses per antigen the p-values will be obtained from an ANOVA model, with vaccination group and center as independent variables and log transformed titers/concentrations as response variable.
  - The null hypotheses will be rejected if the p-values < FWER for all thirteen antigens.
  - For testing Family 2, if the lower limits of the 2-sided 96.67% CIs are greater or equal to the sufficiency margins for each of the four strains and composite endpoint, then Family 2 is successful. Otherwise, Family 2 fails.
- ii. If Family 1 had succeeded and Family 2 not, then propagate  $\frac{1}{2}$  FWER from Family 1 to Family 3 and the other  $\frac{1}{2}$  FWER to Family 2, and re-test Family 2 with the new FWER which is the sum of the original FWER from Family 2 plus the  $\frac{1}{2}$  of FWER from Family 1. If the null hypothesis were rejected during the 2nd time test, then claim the success of Family 2 and propagate full FWER to Family 3; otherwise Family 2 fails and proceed with Family 3 testing with the  $\frac{1}{2}$  of FWER propagated from Family 1.
- iii. If Family 2 had succeeded and Family 1 not, then propagate  $\frac{1}{2}$  FWER from Family 2 to Family 3 and the other  $\frac{1}{2}$  FWER to Family 1, and re-test Family 1 with the new FWER which is the sum of the original FWER from Family 1 plus the  $\frac{1}{2}$  of FWER from Family 2. If the null hypothesis were rejected during the 2nd time test, then claim the success of Family 1 and propagate full FWER to Family 3; otherwise Family 1 fails and proceed with Family 3 testing with the  $\frac{1}{2}$  of FWER propagated from Family 2.
- iv. If both Family 1 and Family 2 had succeeded, then the FWER from both families were propagated to Family 3, and proceed to test Family 3;
- v. If both Family 1 and Family 2 had failed, then no FWER will be propagated to Family 3, and we stop the testing globally and success can be claimed on none of the three families.

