Sufficiency for % of subjects with hSBA titers \geq 8 (for strains M14459, NZ98/254, M13520) and \geq 16 (for strain 96217) individually and all 4 strains combined (composite response) after the 4 th vaccination	>99.999%
Probability of rejection of all 23 null hypotheses.	98.8%

The power was estimated using simulations: 10.000 simulations per case. SAS 9.4 was used for the calculations.

A short summary on the steps of simulation is presented below, in the example of 40% drop-out. The definition for families is given in [Section 9.5.3.1](#).

In total 10.000 simulations were performed, each simulation consisted of:

- For testing Family 1, 240 normal distributed data were drawn for two groups and hence two times thirteen antigens, according to the ratio of GMC and the SD, as described below [Table 18](#). For PCV13, a GMC ratio of 0.8 was assumed. Correlation structure was made for between-antigen correlation of 0%.
- For testing Family 2 and 3, 480 normal distributed data were drawn for one single group and for the four strains, according to the GMTs (for post 3rd dose) and GMTs (for post 4th dose), as shown in [Table 19](#), and the SDs as described below [Table 18](#). Correlation structure was made for between-antigen correlation of 0%.
- Testing of Family 1: Shifted one-sided t-test was used to test the hypotheses and output the p-values (for the power calculation no center effect was assumed).

- d. P-values were compared with the Family Wise Error Rate (FWER) to conclude on whether the null hypotheses were rejected or not. FWER for Family 1 is initially set to be 1/3 of the full alpha, which is rounded to 0.017. The FWER for Family 2 is 0.033 and the initial FWER is 0 for Family 3. No multiplicity adjustment was performed within a family. Within family 1 all thirteen antigens were tested with the full FWER for family 1. If one or more test fail to reject the hypothesis for the antigen, family 1 fails. Consequently the alpha of family 1 will not be propagated (see bullet h. below).

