9.5.3.2. Statistical Methods

For statistical analyses of the concentration/titer data, the concentrations/titers will be logarithmically transformed (base10), to fulfill Gaussian distribution assumption.

The Global Type I error rate will be controlled globally at a 5%/2.5% level (2-/1-sided, respectively). If applicable, the α -level will be propagated as described below [Hommel, 2007]. The sequence of testing the different families is presented in [Figure 2](#) and described in more detail thereafter.

Figure 2 Testing Strategy for Three Families with Corresponding α Propagation

The initial α is 0.0167 (2-sided) for Family 1 and 0.033 (2-sided) for Family 2, while it is zero for Family 3.

Step 1: Family 1 and Family 2

- Start test Family 1 and Family 2 as the first step.
 - For testing Family 1 the hypotheses per antigen the p-values will be obtained from an ANOVA model, with vaccination group and center as independent variables and log transformed titers/concentrations as response variable. The null hypotheses will be rejected if the p-values < FWER for all thirteen antigens.
 - For testing Family 2, if the lower limits of the 2-sided 96.67% CIs are greater or equal to the sufficiency margins for each of the four strains and composite endpoint, then Family 2 is successful. Otherwise, Family 2 fails.
- If Family 1 had succeeded and Family 2 not, then propagate $\frac{1}{2}$ FWER from Family 1 to Family 3 and the other $\frac{1}{2}$ FWER to Family 2, and re-test Family 2 with the new FWER which is the sum of the original FWER from Family 2 plus the $\frac{1}{2}$ of FWER from Family 1. If the null hypothesis were rejected during the 2nd time test, then claim the success of Family 2 and propagate full FWER to Family 3; otherwise Family 2 fails and proceed with Family 3 testing with the $\frac{1}{2}$ of FWER propagated from Family 1.
- If Family 2 had succeeded and Family 1 not, then propagate $\frac{1}{2}$ FWER from Family 2 to Family 3 and the other $\frac{1}{2}$ FWER to Family 1, and re-test Family 1 with the new FWER which is the sum of the original FWER from Family 1 plus the $\frac{1}{2}$ of FWER from Family 2. If the null hypothesis were rejected during the 2nd time test, then claim the success of Family 1 and propagate full FWER to Family 3; otherwise Family 1 fails and proceed with Family 3 testing with the $\frac{1}{2}$ of FWER propagated from Family 2.

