## CONFIDENTIAL

205239 (MENB REC 2ND GEN-023 (V72\_57))

Objectives	Endpoints

 
To demonstrate the sufficiency of the immune response to rMenB+OMV NZ when administered concomitantly with PCV13 and other RIV to healthy infants at 2, 4, 6 and 12 months of age, at one month after the 4th vaccination.
 
 
Criteria: The sufficiency of the immune response to rMenB+OMV NZ will be demonstrated if the adjusted lower confidence limit for the percentage of subjects with hSBA titers <math>\geq 8</math> (for strains M14459, NZ98/254, M13520) and <math>\geq 16</math> (for strain 96217) is <math>\geq 75\%</math> for the individual N. meningitidis serogroup B test strains and is <math>\geq 65\%</math> for all strains combined (composite endpoint).
	
 
At 1 month after the 4th vaccination (Day 331): 
 
the percentages of subjects with hSBA titers <math>\geq 8</math> (for strains M14459, NZ98/254, M13520) and <math>\geq 16</math> (for strain 96217) for each of the test strains.
 
the percentages of subjects with hSBA titers <math>\geq 8</math> (for strains M14459, NZ98/254, M13520) and <math>\geq 16</math> (for strain 96217) for all strains combined (composite endpoint).
 
 
 

 
To demonstrate the immunological non-inferiority of PCV13 when administered concomitantly with rMenB+OMV NZ and other RIV to healthy infants 2, 4 and 6 months of age, compared to PCV13 without rMenB+OMV NZ, at one month after the 3rd vaccination.
 
 
Criterion: The immunological non-inferiority of PCV13 will be demonstrated if the adjusted lower confidence limit for the between-group ratio of electrochemiluminescence (ECL) assay GMCs is <math>>0.5</math> for each of the 13 PCV13 antigens.
	
 
At 1 month after the 3rd vaccination (Day 151): 
 
the ECL GMCs for each of the 13 PCV13 antigens.
 
 
 

Secondary Immunogenicity	

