#### **5.3.1.1. Within groups assessment**

For each study group the following endpoints will be assessed related to MenB strains and PCV13 strains:

- the percentage of subjects with hSBA titers  $\geq$  LLOQ for each of the M14459, 96217, NZ98/254 and M13520 test strains and for all strains combined, at each timepoint that a blood sample result will be available
- the percentage of subjects with hSBA titers  $\geq 5$ ,  $\geq 8$  and  $\geq 16$  for each of the M14459, 96217, NZ98/254 and M13520 test strains, at each timepoint that a blood sample result will be available
- the percentages of subjects with hSBA titers  $\geq 8$  for each of the test strains (M14459, NZ98/254 and M13520),  $\geq 16$  for test strain 96217, and for all strains combined (composite endpoint) at one month after the 4th vaccination

- the percentage of subjects with 4-fold increase at post-4th (from pre-4th vaccination) for each of the M14459, 96217, NZ98/254 and M13520 test strains
- GMCs/GMTs and within group GMRs (for post-4th versus pre-4th titers) will be tabulated for antibodies for each antigen, at each timepoint that a blood sample result will be available
- Percentage of subjects with serum pneumococcal anti-capsular polysaccharide IgG  $\geq 0.35$   $\mu$ g/mL at one month after the 3rd and 4th vaccination in Group MenB+PCV and Group Placebo+PCV.

The CIs will be calculated as 2-sided 95% for exploratory objectives and will be calculated at given alpha at the testing step for the primary objectives that are associated with statistical hypothesis testing.

Endpoints associated with the other RIV will be assessed within-group as specified in Section 3. The 2-sided 95% CIs will be calculated.

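### The Family 1 rule compares p-values of unstated sidedness with a two-sided alpha, and the Step 3 re-test, read literally, can never succeed

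*SAP*

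**What the plan says.** - **Decision rule.** SAP 5.3.1.3, Step 1, takes p-values from an ANOVA with group and center, then states: "The null hypotheses will be rejected if the p-values < FWER for all thirteen antigens". Protocol 9.5.3.2 has the same rule. Neither gives the sidedness.
- **Hypothesis.** The Family 1 null is one-directional, with margin log10(0.5): "Non-inferiority will be claimed if the following null hypothesis will be rejected for the 13 PCV13 antigens".
- **Alpha.** The note to SAP Figure 2 sets the initial alpha at "0.0167 (2-sided) for Family 1 and 0.0333 (2-sided) for Family 2". Protocol 9.5.3.2 states the overall control: "The Global Type I error rate will be controlled globally at a 5%/2.5% level (2-/1-sided, respectively").
- **Success criterion.** SAP section 3 declares non-inferiority "if the adjusted lower confidence limit for the between-group ratio of electrochemiluminescence (ECL) assay GMCs is" above 0.5 for each of the 13 antigens. SAP 5.3.1.1 says that CIs "will be calculated at given alpha at the testing step for the primary objectives that are associated with statistical hypothesis testing".
- **Family 2, same list.** Its rule is explicit: the lower limits of two-sided 96.67% CIs.
- **Power simulation.** Protocol 9.1, step c: "Shifted one-sided t-test was used to test the hypotheses and output the p-values". Step d compares these p-values with a Family 1 FWER of one third of the full alpha, rounded to 0.017.
- **Step 3.** If Family 3 succeeds, a family that failed earlier may be tested again with half of Family 3's FWER. The text does not say whether that share is added to the alpha the family already holds.

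**The concern.** A programmer working from the Family 1 bullet must choose the sidedness. A one-sided p tested at half the two-sided alpha agrees with the adjusted-CI criterion. A one-sided p tested at the printed 0.0167 is twice as lenient, and protocol 9.1 describes that comparison for the simulation. A co-primary could then pass by p-value while failing the CI criterion in the objectives, and the stated 2.5% one-sided control would not hold. At Step 3, one reading gives a usable re-test and the other gives a step that cannot change any result. Both choices should be fixed before anyone can see which one matters.

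**Working it through.** **Inputs.** 240 evaluable per group, true GMC ratio 0.8, between-antigen correlation 0 (protocol 9.1). SDs from protocol Table 18: 19F is the largest at 0.45638 and 6B is 0.44974. df = 478; SE = SD × sqrt(2/240).

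**1. The plan's own power figure.** The shift is log10(0.8) − log10(0.5) = 0.2041. Power for all 13 antigens is the product of non-central t powers. At one-sided 0.017 it is 99.27%, against 99.0% in Table 17. At one-sided 0.00833 it is 98.29%. Both are within a point of the stated value.

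**2. One-sided level under each rule.**
- CI rule, Step 1: 0.0167/2 = 0.0083 (98.33% CI).
- One-sided p against the printed alpha, Step 1: 0.0167, a factor of 2.
- Re-test after Family 2 succeeds: Family 1 holds 0.0167 + 0.0333/2 = 0.0333 two-sided. That is 0.0167 one-sided under the CI rule (96.67% CI) and 0.0333 under the unhalved rule.

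**3. Step 1 type I error.** Assume one Family 1 antigen and one Family 2 endpoint at their margins, independent, with everything else passing.
- Unhalved: 1 − (1 − 0.01667)² = 3.31%.
- CI rule: 1 − (1 − 0.00833)(1 − 0.01667) = 2.49%.
- Stated: 2.5%.

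**4. Smallest observed ratio that passes,** 0.5 × 10^(t × SE):

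| One-sided level | 19F | 6B |
|---|---|---|
| 0.00833 | 0.6296 | 0.6275 |
| 0.01667 | 0.6136 | 0.6118 |
| 0.03333 | 0.5964 | 0.5949 |

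After the re-test the rules disagree for an observed 19F ratio between 0.596 and 0.614, and for 6B between 0.595 and 0.612.

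**5. How often this matters.** At a true ratio of 0.8, power with the re-test is 99.25% (CI rule) and 99.72% (unhalved), a difference of 0.47 point. For 19F alone, given Family 2 success, the chance of passing only the unhalved rule is 10.7%, 11.7% and 11.4% at true ratios of 0.58, 0.60 and 0.62.

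**6. Step 3 after Family 2 succeeds and Family 1 fails.** Family 3 receives 0.0333/2 = 0.0167; if it succeeds, half of that is 0.0083.
- Share used alone: 0.0083 two-sided (99.17% CI). 19F needs 0.6447, but it has already failed at 0.6136, so this can never succeed.
- Share added: 0.0333 + 0.0083 = 0.0417 two-sided (95.83% CI). 19F needs 0.6082, a real second chance.

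The mirror case behaves the same way. If Family 1 succeeds, Family 2 has failed at 0.0333 + 0.0083 = 0.0417, and the share from Family 3 is 0.0083/2 = 0.0042.

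**The case against.** The strongest reply is that the analysis text already settles the rule. The alpha is labelled two-sided just before the bullet, SAP section 6 repeats two-sided control, the objective is an adjusted confidence limit, and Family 2 in the same list uses a two-sided CI. This largely stands: the CI reading is the better one, and under it there is no inflation. It does not remove the gap. The bullet is the operative rule, the 98.33% level is not printed for Family 1, and the only sidedness given for the p-value points the other way.

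Four stronger inferences are tempting, and the documents do not support them.

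- *The analysis will run at double the level.* Protocol 9.1 records a power simulation. Nothing carries its steps c and d into the analysis.
- *The simulation deliberately left alpha unhalved.* Step d says "Within family 1 all thirteen antigens were tested with the full FWER for family 1", but the sentence before it is about multiplicity within a family. Here full means not split across the 13 antigens.
- *Table 17 confirms the lenient level.* It does not. Step h of 9.1 includes the re-test and Family 2 power is above 99.999%, so the relevant figures are 99.72% unhalved and 99.25% under the CI rule. The stated 99.0% is closer to the latter. Step 1 alone at 0.017 gives 99.27%, so the table settles nothing either way.
- *The 10.7 to 11.7% are false positives.* True ratios of 0.58 to 0.62 lie above the 0.5 margin. These are differences in power.

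The 3.31% is also a worst case. With two independent antigens at the margin, the unhalved Step 1 figure is 1 − (1 − 0.01667²)(1 − 0.01667) = 1.69%, below 2.5%.

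On Step 3, one can argue that addition is the only workable reading, since Step 1 ii and iii define re-test levels as sums. That supports adding the share, but Step 3 itself does not say so.

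**Conclusion.** The point holds as an ambiguity in a co-primary decision rule that should be fixed. It does not show that type I error is inflated. The Family 1 bullet omits the sidedness. The documents favour the lower limit of a two-sided 98.33% CI above 0.5, and only that rule, or a one-sided p below half of alpha, keeps the stated 2.5%. Carrying the protocol 9.1 convention into the analysis would give 3.31% at Step 1, assuming exactly one antigen and one Family 2 endpoint at their margins and independence between them. At the design ratio of 0.8, with 240 per group and Table 18 SDs, the practical difference after the re-test is about 0.5% of trials. Which level the simulation used cannot be determined. Step 3 is a separate defect of definition: its literal level is stricter than the test already failed, so the step does nothing.

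**What to change.** In the SAP, before unblinding, replace the Family 1 bullet with:

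> Family 1 succeeds if, for all 13 antigens, the lower limit of the two-sided 100(1 − alpha)% CI of the ANOVA GMC ratio is > 0.5, where alpha is the two-sided alpha held by Family 1 at that step (98.33% CI at Step 1, 96.67% CI at the re-test after Family 2 succeeds); equivalently, the one-sided p against log10(0.5) is < alpha/2.

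CI wording is safer than writing two-sided p-value, because a two-sided p is also small when the ratio lies clearly below 0.5.

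State that at Step 3 the share from Family 3 is added to the alpha already held. For Family 1 after Family 2 succeeds this is 0.0417 two-sided (95.83% CI). For Family 2 after Family 1 succeeds it is 0.0417 + 0.0042 = 0.0458 (95.42% CI).

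Align protocol 9.5.3.2 at the next amendment. The simulation record in protocol 9.1 need not be rewritten. It is enough to confirm that about 99% stands under the CI rule (recomputed 98.3% at Step 1, 99.25% with the re-test).

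The cost is two sentences in the SAP, a protocol alignment and a check of Table 17. No extra subjects are needed, and the power given up relative to the unhalved convention is about 0.5 point with the re-test.

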**Step 2: Family 3**

If all null hypotheses are rejected, then propagate 1/2 FWER to Family 1 and Family 2 respectively, and success can be claimed for Family 3, as well as for Family 1 and/or Family 2 whichever was successful in Step 1; otherwise stop testing globally, and success can be claimed for Family 1 and/or Family 2 whichever was successful in Step 1.

**Step 3: Family 1 or Family 2**

In case one of Family 1 and Family 2 failed in step 1, with the alpha passed down by Family 3, it is possible to re-test the family that failed once and again test it with  $\frac{1}{2}$  FWER from Family 3. If all null hypotheses are rejected, then success can be claimed for this family as well.

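### Step 3 of the primary testing procedure does not say that alpha from Family 3 is added to what the failed family already holds; read literally it cannot change a decision, and read additively it still falls short of 0.05

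*SAP*

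**What the plan says.** The three families share a global two-sided 5%. The SAP gives the starting split under Figure 2 as "0.0167 (2-sided) for Family 1 and 0.0333 (2-sided) for Family 2, while it is zero for family 3".

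Step 1 spells out how a failed family is re-tested once the other has succeeded. Family 1 is re-tested at a "new FWER which is the sum of the original FWER from Family 1 plus the" half passed on by Family 2, and Family 2 at a "new FWER which is the sum of the original FWER from Family 2 plus the" half passed on by Family 1. If the re-test also fails, Family 3 is tested with the other half only.

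Step 2 covers success of Family 3. Half of its FWER goes to each of Families 1 and 2, and "success can be claimed for Family 3, as well as for Family 1 and/or Family 2 whichever was successful in Step 1". One of those two has by then already been rejected, so its half has no use.

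Step 3 returns to the family that failed: "it is possible to re-test the family that failed once and again test it with" half of Family 3's FWER. No sum is mentioned. Protocol 9.5.3.2 has the same Step 3 wording.

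**The concern.** Step 3 exists for one situation: a co-primary family narrowly misses while the other two succeed. The plan says success may then still be claimed for it. If the re-test level is only the half received from Family 3, it is stricter than levels the family has already failed, and the step does nothing. If the half is meant to be added, the step works, but part of the 5% is left unused. A programmer cannot tell from the text which to code. The level for a co-primary claim should not be open to choice once results are known.

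**Working it through.** **Inputs.** Starting levels 0.05/3 = 0.0167 (Family 1), 0.10/3 = 0.0333 (Family 2) and 0 (Family 3), from the SAP under Figure 2. They sum to 0.05, and 1 − 0.0333 reproduces the 96.67% interval in Step 1. The transfer weights are one half throughout, from Steps 1 and 2. Exact thirds are carried below.

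**Levels in the two branches.**

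| | Family 1 failed, Family 2 succeeded | Family 2 failed, Family 1 succeeded |
|---|---|---|
| First test | 0.0167 | 0.0333 |
| Step 1 re-test | 0.0167 + 0.0333/2 = 0.0333 | 0.0333 + 0.0167/2 = 0.0417 |
| Family 3 tested at | 0.0333/2 = 0.0167 | 0.0167/2 = 0.0083 |
| Step 3, literal | 0.0167/2 = 0.0083 | 0.0083/2 = 0.0042 |
| Step 3, additive | 0.0333 + 0.0083 = 0.0417 | 0.0417 + 0.0042 = 0.0458 |
| Step 3, graphical update | 0.0333 + 0.0167 = 0.05 | 0.0417 + 0.0083 = 0.05 |

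A p-value above 0.0333 is also above 0.0083, and a lower confidence limit only moves down as alpha shrinks. On the literal reading the family therefore fails again in both branches.

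**Why 0.05 is available.** A family succeeds only if every one of its hypotheses is rejected, so each family acts as a single hypothesis in a three-node graph. When a family r has been rejected, the standard update of the weight from Family 3 to the remaining family k is

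(w3k + w3r·wrk) / (1 − w3r·wr3) = (1/2 + 1/4) / (1 − 1/4) = 1.

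All of Family 3's alpha then goes to the remaining family. Step 1 already works this way in the other direction: once one of Families 1 and 2 has succeeded and the other passes its re-test, the text sends full FWER to Family 3, with nothing returned to a family already rejected.

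**Family 1 pass rates.** Inputs from Protocol 9.1: 240 per group, Table 18 SDs, margin 0.5, planned GMC ratio 0.8, 13 independent antigens. Power per antigen is P(T > t) with 478 degrees of freedom and noncentrality log10(ratio/0.5) / (SD·√(2/240)); the 13 values are multiplied. For 19F at ratio 0.8: 0.2041 / (0.45638 × 0.09129) = 4.90. As a check against the 99.0% in Table 17, this gives 99.3% with 0.017 taken as one-sided and 98.3% with 0.017 taken as two-sided. The figures below treat each level as two-sided.

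| GMC ratio, all antigens | 0.0333 | 0.0417 | 0.05 |
|---|---|---|---|
| 0.80 (planned) | 99.2% | 99.4% | 99.6% |
| 0.75 (assumed) | 94.4% | 95.6% | 96.4% |
| 0.70 (assumed) | 69.9% | 74.6% | 78.1% |

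The 0.0333 column is also what the literal Step 3 delivers, since it adds nothing.

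**Family 2 in counts.** With 480 infants and Clopper-Pearson limits (assumed here), the smallest passing counts (single strain at 75% / composite at 65%) are 380 / 334 at 0.0417, 380 / 334 at 0.0458, 379 / 333 at 0.05 and 388 / 343 at 0.0042. At exactly this sample size the additive level changes nothing for Family 2, and the full 0.05 is worth one infant.

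**The case against.** The best defence is that the additive reading is the natural one. Step 1 shows that alpha received is added to alpha held, Step 2 uses the same idea of propagation, and Step 3 refers to alpha handed down by Family 3. Read consistently, the step can rescue a family. This stands as far as it goes: a reader might infer from the literal wording that Step 3 can never rescue anything, but that holds only on the literal reading, and the documents do not settle which was meant. It does not remove the gap, because Step 1 states the sum for both families and Step 3 omits it, and the additive levels still stop at 0.0417 and 0.0458.

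A reader might also infer that the plan departs from its own cited method. That goes too far. Only the SAP cites the graphical approach; the protocol cites a paper on short-cut and gatekeeping procedures. Neither source was consulted, and Figure 2 might carry weights that resolve the matter. The 0.05 above rests on the weights in the text and the general update rule.

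Finally, the practical effect is small. At the planned ratio the gain is about 0.3 points over the literal reading. The tabulated gains are also upper bounds, because Families 2 and 3 must succeed before Step 3 is reached for Family 1. That condition can bind: with the SAP 5.3.2 LLOQs (6 for M13520, 14 for 96217), the Table 18 and 19 inputs, independent strains and 480 infants, simulation passes Family 3 in about 68% at 0.0167, against essentially 100% with the Protocol Table 20 LLOQs.

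**Conclusion.** The point holds as an unclear and inefficient rule. Step 3 does not say whether alpha is added. Literally it is inert; additively it leaves 0.0083 (Family 1) or 0.0042 (Family 2) of the 5% unspent. With the weights in the text, 0.05 is available in both branches.

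Two stronger inferences are not supported. Type I error is not inflated: every reading stays within two-sided 5%. The planned power is not overstated either: the simulation steps in Protocol 9.1 end with Family 3 and include no Step 3 re-test, so Table 17 and the sample size are untouched.

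For Family 1, moving from 0.0333 to 0.05 gains at most about 0.3 points at ratio 0.8, 2.0 at 0.75 (96.4 − 94.4) and 8.2 at 0.70 (78.1 − 69.9). The last two ratios are assumptions applied to all 13 antigens at once; no document gives them. The matter is worth correcting because the step is needed only in a near miss, and that is when an unstated level would be disputed.

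**What to change.** In SAP 5.3.1.3 and Protocol 9.5.3.2, replace the Step 3 rule with: if Family 3 and one of Families 1 and 2 have succeeded, the remaining family is re-tested at its current level plus the full FWER of Family 3, i.e. two-sided 0.05. Amend Step 2 so that no alpha is sent to a family already rejected, and check that Figure 2 agrees.

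The cost is a sentence or two in each document, made before unblinding. Family-wise error stays at two-sided 5%, and design, sample size and conduct do not change.
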